10.2.4 Safety Analysis Set

The Safety Analysis Set (SAF) will include all randomized subjects who receive at least one dose of study treatment. Subjects will be analyzed according to the actual treatment they receive during the study. All safety and subject-level PK analyses will be performed using this analysis set.

10.2.5 PK Analysis Set

The Pharmacokinetic (PK) Analysis Set will include all subjects who:

- receive at least one dose of study treatment and
- have at least one valid post-dose pharmacokinetic assessment.

Important events which may impact the quality of the PK data include, but may not be limited to, sample processing errors that lead to inaccurate bioanalytical results, and/or inaccurate dosing on the day of PK sampling. In the case of such events, PK samples collected during the affected treatment will be excluded from descriptive statistics, but will still be included in the listings.

Analyses exploring associations between (observed) PK and immunogenicity, and between (observed) PK and efficacy, will also use the PK Analysis Set.

Subjects in the PK Analysis Set will be analyzed according to the actual treatment received during the study.

10.2.6 Subgroups

Subgroup analyses will be performed for the secondary endpoints ACR20 and ACR50 (insufficient data expected for ACR70) on subgroups as defined below, using the ITT analysis set.

The following subgroups will be defined:

- Previous Systemic Therapy Use
 - Biological
 - Non-biological only
- Age
 - < 65 years
 - \geq 65 years
- Sex
 - Male
 - Female
- Weight
 - < 90kg
 - $\geq 90 \text{ kg}$
- BMI
 - $< 25 \text{ kg/m}^2$
 - $\geq 25 \text{ kg/m}^2 < 30 \text{ kg/m}^2$
 - $\geq 30 \text{ kg/m}^2$

- Race
 - White
 - Other
- Ethnicity
 - Hispanic or Latino
 - Not Hispanic or Latino
- Time since first diagnosis of rheumatoid arthritis
 - <5 years
 - \geq 5 years

11 General Specifications for Statistical Analyses

Descriptive statistics will be given with reference to the analysis set deemed appropriate for each particular endpoint. Unless otherwise indicated, all analyses/summaries will be presented by the two treatment arms, MSB11022 and Humira. Note that this document refers to treatment arms; however, the output shells present 'treatment group', as defined in the standard templates.

All statistical analyses will be performed using SAS® Version 9.2 or higher.

11.1 Descriptive Methods

Descriptive statistics for continuous data will include the following:

- Number of subjects with non-missing data (n)
- Number of subjects with missing data
- Mean, standard deviation (SD)
- Median, first and third quartiles (Q1 and Q3)
- Minimum and maximum
- 95% confidence interval (CI).

All statistics will be rounded according to Merck's Global Biostatistics Output Standards (GBSOS) Booklet (Version 4.0 or later), ie, percentages will be rounded to one decimal. The mean, median, Q1, Q3, and 95% CI will be presented with one additional decimal compared to the raw data; SD will be presented with two additional decimals compared to the raw data; and minimum and maximum will be presented with the same number of decimals as the raw data.

All data will be presented by nominal visit (including the safety follow-up visits – four weeks and four months after the last dose of IMP) and no visit windowing rules will be implemented. Data from unscheduled visits will be listed but will not be included in summaries presented by

visit. The exceptions will be in the calculation of the baseline values. Data from unscheduled visits will also be included in the calculation of the worst on-treatment values and grades.

Categorical data will be summarized by presenting the number of subjects with non-missing data (n), the number of subjects with missing data (missing), and the number and percentage of subjects in each category. Percentages will be based on the number of subjects with non-missing data in the analysis set of interest, unless otherwise specified.

Time to event variables will be summarized by presenting Kaplan Meier estimates and 95% CIs.

Change from baseline will be calculated as the post-baseline value minus the baseline value. Percent change from baseline is defined as (100 x (post-baseline – baseline) / baseline).

If all baseline values are missing for a particular variable, the change from baseline and percent change/percent improvement from baseline will not be calculated.

A 2-sided significance level of 5% will be used for all analyses. Two-sided 95% confidence intervals will be calculated.

11.2 Inferential Methods

There will be no adjustment for multiple testing because there are only two treatment arms and a single primary endpoint. All other analyses (key secondary and other secondary endpoints) are considered as supportive to the primary endpoint.

11.3 Listings

All data will be presented in subject listings. All listings produced for the analyses will be ordered by treatment arm (MSB11022, Humira), subject identifier, visit, and date, unless otherwise specified.

Planned treatment arms will be presented except for treatment exposure and safety listings where actual treatment will be shown.

11.4 Handling of Missing Data

For historical data collected at screening, partial dates will not be imputed. The exception is deriving time from diagnosis in months where the 1st of the month is imputed if day is missing, and the 1st January is imputed if both day and month are missing. These imputed dates will not be shown in the corresponding listing.

The handling of partial dates of birth is covered in the Demographics Section 12.2. Handling of partial or missing dates for concomitant medications and AEs is covered in Sections 13 and 16.1 of this SAP, respectively. Handling of missing date/time for study drug related injection site reaction analysis is covered in Section 16.1.1.

No imputation will be performed for PK or immunogenicity data.

11.4.1 Imputation Methods for Key Secondary Endpoint

The analysis of ACR20 at Week 12 on the ITT analysis set will be repeated using a non-responder method to impute any missing data. This method will classify a subject with missing ACR20 at Week 12 as a non-responder at that timepoint.

An imputation for withdrawal will also be performed, defined as follows: if a subject discontinues prematurely prior to Week 12, the ACR20 will be imputed as a non-responder, while subjects who complete the study but have a missing assessment for ACR20 at Week 12 will not be imputed.

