### 7.1.2 Baseline Assessments and Treatment Period

During the 52-week period, patients will be asked to visit the trial site at the visits indicated in the Schedule of Assessments (Table 1). Except for the Day 1/Week 0 (baseline) visit, a time window of up to 2 days before or after ( $\pm 2$  days) the scheduled day will be permitted for all trial visits during the treatment period.

Demographics, medical history, and inclusion/exclusion criteria will be reviewed to ensure that patients remain eligible for the trial.

An Emergency Medical Support card will be handed out on Day 1/Week 0 (baseline).

The IWRS will be contacted on Day 1/Week 0 (baseline) for patient randomization after all eligibility criteria have been confirmed. Patients will be randomized to receive either 40 mg MSB11022-CCI or 40 mg Humira® every other week starting on Day 1/Week 0 (baseline) and continuing up to and including Week 48. If the IMP is well tolerated as per medical judgment, and reflects the expected safety profile during these visits, the remainder of the patients will be dosed. The IMP is administered at the trial site for the first 3 doses; at Weeks 0, and 2, the patient or a caregiver will be trained for self-injection/injection and at Week 4, the patient will self-inject. Patients will be monitored for 1 hour following IMP administration on Day 1/Week 0, Week 2, and Week 4. Patients or their caregivers will administer the IMP for all subsequent doses and record the dosing date and time in a diary.

Patients who achieve less than 20% improvement in both swollen and tender joint counts at Week 24 (non-responders) will be discontinued from IMP and must immediately perform the assessments listed for the early termination visit and return for the safety follow-up visit 4 weeks after the last dose of IMP in addition to a safety follow-up visit 4 months after the last dose of IMP.

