The first 2 doses of IMP will be administered on site by the Investigator or other qualified personnel and the patient will be educated on the correct process. The third dose of IMP will be administered on-site by the patient. Patients will be monitored for 1 hour following the first 3 IMP administrations. If the Investigator judges it appropriate after proper training, the patient (or a caregiver) may continue to self-inject/inject the treatment for the remaining doses. Injection site pain will be assessed after doses 3 to 5. If a patient self-administers, the injection should not be given in the arm. The remaining doses of IMP will be dispensed, and written instructions on proper dosage, administration, storage, and recording will be provided to the patient/care-giver. Administrations performed at home will be recorded in a diary with the accurate dosing information (dosing date and time).

The 52-week double-blind period will allow for the collection of long-term comparative safety, immunogenicity, and efficacy data for MSB11022-CCI versus Humira.

Subjects who achieve less than a 20% improvement in both swollen and tender joint counts at Week 24 (non-responders) will be discontinued from the IMP. These subjects will remain in the trial safety analysis set and participate in the safety and immunogenicity assessments. After Week 24, patients with less than 20% improvement in both swollen and tender joint counts at any scheduled visit up to Week 52 will also be discontinued. Subjects may continue at Investigator discretion from Week 24 to Week 52 as long as they maintain 20% or more improvement in both swollen and tender joint counts.

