Patients who discontinue from study medication (but remain in the trial and continue for the safety/immunogenicity visits) before the Week 52 visit will immediately complete an Early Termination visit and return for a Safety/Follow-up visit four weeks after the last dose of IMP. During this 4-week Safety Follow-up period, no excluded treatment for RA (as defined in the protocol) should be administered. Patients will return for an additional safety evaluation four months after the last dose of IMP. Treatment for RA from the 4-week Safety Follow-up visit to the 4-month Safety Evaluation visit will be at the discretion of the Investigator following institutional standard of care. The 4-week and 4-month Safety Follow-up visits will not be duplicated if either of these visits falls within two weeks of an otherwise scheduled visit. If the 4-week and 4-month Safety Follow-up since last IMP are completed within the 52 week visit schedule, these will not be repeated thereafter.

All subjects will have PK samples taken pre-first dose, and then prior to dosing on Weeks 2, 4, 12, 24, 36 and 52. In addition, a subset of 60 subjects (30 per arm) will have additional samples to support the population PK analysis taken on Days 2 (24 h post first dose), 4, and 9, and Days 2 (24 h post Week 24 dose), 4, 9, and 14 (Week 26 pre dose) after the Week 24 dose.

The anticipated duration of the entire trial is approximately two years.

Visit schedules for safety, immunogenicity, and efficacy assessments are detailed in the

Schedule of Assessments in the protocol.

Planned number of patients: Approximately 260 randomized subjects

Primary endpoint:

• Treatment-emergent adverse events of special interest (AESI) including and up to Week 52

Secondary endpoints:

Key secondary endpoint

• American College of Rheumatology 20% response criteria (ACR20) at Week 12. An ACR20 response is defined as an improvement of at least 20% in the number of tender joints and swollen joints, and at least 20% improvement in three out of the remaining five ACR core-set measures: patient assessment of arthritis pain, Patient's and Physician's Global Assessment of Disease Activity, physical function via the Health Assessment Questionnaire-Disability Index [HAQ-DI] and acute-phase reactant as measured by C-reactive protein (CRP).

Other secondary endpoints

Safety

- Occurrences of treatment-emergent adverse events (TEAEs) and serious adverse events (SAEs) including and up to Week 52

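### The Week 52 response rates labelled ITT are observed-case, so patients taken off treatment at Week 24 as joint-count failures drop out of the denominator

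*SAP*

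**What the plan says.** SAP 11.1 sets the default denominator: "Percentages will be based on the number of subjects with non-missing data in the analysis set of interest, unless otherwise specified". It also tabulates "the number of subjects with missing data (missing), and the number and percentage of subjects in each category", presents data by nominal visit, and states that "no visit windowing rules will be implemented".

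SAP 11.4.1, which is headed for the key secondary endpoint, adds two variants, both tied to Week 12. The first reads: "The analysis of ACR20 at Week 12 on the ITT analysis set will be repeated using a non-responder method to impute any missing data". The second counts as non-responders those who discontinue before Week 12, "while subjects who complete the study but have a missing assessment for ACR20 at Week 12 will not be imputed".

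SAP 15.2.2.1 and 15.2.2.2 analyse ACR20 at other visits, and ACR50/70, in the manner of SAP 15.2.1, which refers to 11.4.1 for missing data. SAP 15.2.2.4 (DAS28 low activity and remission) and 15.2.2.7 (Boolean remission) contain no such reference. Protocol 8.7 had promised that the SAP would cover missing data for all secondary endpoints.

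Under Protocol 7.1.2, Week 24 joint-count non-responders "will be discontinued from IMP and must immediately perform the assessments listed for the early termination visit". SAP 6 says of them: "These subjects will remain in the trial safety analysis set and participate in the safety and immunogenicity assessments". SAP 8 ends the data of subjects who stop treatment early at theoretical Week 52 or the 4-month safety visit, whichever is earlier.

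**The concern.** The ITT set is defined as all randomised patients, but the main binary efficacy rates use only those with a value at the visit. At Week 52 the absentees are not a random subset. Some were removed by a rule that selects patients for poor joint response. Leaving them out raises the ACR response rate in each arm relative to counting them as failures, and the rate can rise between Week 24 and Week 52 without any patient's response changing.

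Comparing efficacy up to Week 52 is a stated secondary objective (Protocol 4.2.2). If the rule removes more patients in one arm than in the other, the arm with more failures gains. No imputed Week 52 rate or interval is expressly planned to show this.

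**Working it through.** The plan gives no figure for Week 52 efficacy, the share stopped under the rule, or missing ACR data, so there is nothing of its own to reproduce here. From the documents come 130 patients per arm and 20% planned dropout (Protocol 8.1), and 1 month = 30.4375 days (SAP 11.8). Responder counts and stopping shares are assumptions.

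**1. Are stopped patients ACR failures?** ACR20 needs at least 20% improvement in both joint counts (SAP 15.2.1). The stopping rule is worded differently in Protocol 5.2 and in footnote a of Table 1, and the two should be reconciled. On either wording the patient lacks 20% improvement in at least one count, and so fails ACR20, ACR50 and ACR70 when stopped.

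**2. Boolean remission and DAS28.** Entry requires at least 6 swollen and 6 tender joints on the 66/68 count (Protocol 5.3.1). As 6 × 0.8 = 4.8, less than 20% improvement leaves at least 5 joints, against a limit of 1. On that count the patient fails Boolean remission. DAS28 status is not fixed by the rule.

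**3. When does the rule remove patients?** It applies from Week 24 at any scheduled visit, but the only efficacy timepoint after Week 24 is Week 52 (Protocol 8.3.2). Removals therefore arise essentially at Week 24.

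**4. Is there a Week 52 value?** Four months is 4 × 30.4375 = 121.75 days, and 121.75/7 = 17.4 weeks. A last dose at Week 22 or 24 puts the 4-month visit at Week 39.4 or 41.4. The ±1 week window does not bring it near Week 52, so the SAP 8 cut falls well before it. Without windowing, the early termination assessment does not move to Week 52. The patient is missing there.

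**5. Size.** Let N be the number randomised, k the number missing and R the responders. If the missing count as non-responders,

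observed-case rate = R/(N − k) = (R/N) × N/(N − k).

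With N = 130 and R = 73 (73/130 = 56.2%, exact 95% CI 47.2 to 64.8):

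| k missing | share | factor | observed-case rate | excess |
|---|---|---|---|---|
| 7 | 5.4% | 130/123 = 1.06 | 59.3% | +3.2 points |
| 13 | 10.0% | 130/117 = 1.11 | 62.4% (CI 53.0 to 71.2) | +6.2 points |
| 20 | 15.4% | 130/110 = 1.18 | 66.4% | +10.2 points |

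These rows assume that everyone else is observed at Week 52. At other response levels with k = 13, 52/130 = 40.0% becomes 52/117 = 44.4%, and 91/130 = 70.0% becomes 91/117 = 77.8%. If the whole planned 20% dropout (26 per arm) became missing response, the factor would be 130/104 = 1.25, and 56.2% would become 70.2%.

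**6. Between arms.**
- Equal missing shares, 78 against 65 responders: 13/130 = 10.0 points becomes 13/117 = 11.1 points at 10% missing and 13/104 = 12.5 at 20%. A true zero stays zero.
- Unequal shares, 73 responders in each arm, 7 against 20 stopped: 73/123 = 59.3% against 73/110 = 66.4%, a spurious 7.0-point difference (from unrounded rates) in favour of the arm with more failures.

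**The case against.** The strongest reply is that the cross-references already deal with ACR. SAP 15.2.2.1 and 15.2.2.2 send the reader to 15.2.1, which sends the reader to 11.4.1, so the non-responder repeat may be meant for every ACR endpoint and visit. That reading is possible, but it ends in rules worded only for Week 12, and imputation would still be a repeat beside an observed-case main rate. The withdrawal variant does not say how to class a patient who stops IMP but stays in the trial. DAS28 and Boolean remission have no link to 11.4.1 at all.

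The absence of a Week 52 value is also an inference. No sentence says that efficacy assessment ends, Protocol 5.4.2 keeps these patients in follow-up to the end of the trial, and Table 1 as extracted cannot settle the matter. The inference still holds, because a Week 52 value, even if collected, would lie beyond the SAP 8 cut.

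Several points stand:
- Every magnitude is assumed. The 20% dropout concerns presence in the study, which is a different group from patients stopped for joint counts.
- No inflation is shown for DAS28.
- At Week 24 the stopped patients are observed and counted as failures, so the demonstrated harm is at Week 52.
- Non-responder imputation shrinks differences between arms, which in a biosimilar comparison makes them look more alike.
- The SAP offers partial safeguards: missing counts, discontinuation reasons by arm (12.1), full listings, and a time-to-ACR20 analysis on the ITT set. A reader could rebuild the imputed proportion from the counts, but no such rate or interval is expressly planned.

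**Conclusion.** The concern holds. Followed as written, the SAP removes known ACR failures from Week 52 rates labelled ITT. Counting them as non-responders, the observed-case rate is too high by a factor of 1.06 to 1.18 for assumed stopping shares of 5.4% to 15.4%. At 56.2% that is 3.2 to 10.2 points.

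This is a statement about a non-responder definition, not about true Week 52 status. That status is unknown: "Treatment for RA from the 4-week Safety Follow-up visit to the 4-month Safety Evaluation visit will be at the discretion of the Investigator", and other patients stop for reasons unrelated to efficacy (Protocol 5.4.1). The between-arm difference is seriously distorted only if missing shares differ.

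The primary AESI endpoint and ACR20 at Week 12 are untouched by the Week 24 rule. The affected endpoints are secondary and descriptive, so no error rate or decision rule is involved. The importance is minor to moderate, and the point should be fixed because the remedy is cheap.

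**What to change.** In SAP 11.4.1 and 15.2.2:
- State the missing-data rule for each binary efficacy endpoint and visit, as Protocol 8.7 promised.
- Add a non-responder analysis with all randomised subjects in the denominator, with its confidence intervals, for ACR20/50/70, DAS28 low activity and remission, and Boolean remission. Week 52 is where it matters; Week 24 can be included for consistency.
- Count patients stopped under the joint-count rule as non-responders at later visits. For DAS28 this is a convention and should be described as one.
- State how other IMP discontinuations are counted, including patients who stop IMP but remain in the trial.
- Report the present rate alongside and label it observed-case, not only ITT.

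The cost is SAP wording and extra tables, with no new data. The added analysis counts some patients who left for reasons unrelated to efficacy as failures, which is why both results should be shown together.

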11.5 Data handling after cut-off date

Details can be found in Section 8.

11.6 Trial Day

Trial Day 1 is defined as the day on which the first dose of study treatment is administered (Day 1/Week 0), or the day of randomization for ITT subjects who did not receive any study treatment. All other trial days will be calculated relative to that date. For example, the day before the start of study treatment is Day -1 (there is no Day 0).

11.7 Baseline Definitions

Baseline is defined as the last non-missing assessment prior to or on Trial Day 1. Exceptions are assessments on the date of first dose of trial treatment where assessment time is or should be reported. In these situations: if the time is before the treatment start time then the assessment is baseline, if the time is after the treatment start time then the assessment is post baseline. If the time is at the same time as starting treatment and is from a scheduled Screening or Day 1/Week 0 assessment then the assessment is baseline, otherwise it is post baseline. If the time is missing and there is no available baseline value meeting the prior criteria then the value will be used as baseline if it is from a scheduled Screening or Day 1/Week 0 assessment. These baseline data will be used in all demographic and baseline summaries.

For vital signs that have been measured twice at the same visit, the average value per visit will be calculated before determining the last non-missing assessments to use as the baseline.

11.8 Data Derivation

The following conversion factors will be used to convert days to months or years, where applicable:

- 1 month = 30.4375 days
- 1 year = 365.25 days.

See Section 12.2 for the calculation of subject age.

Duration will be calculated by the difference of start and stop date + 1 (eg AE duration (days) = stop date of AE – start date of AE + 1) (if not otherwise specified). Durations are calculated only when both dates are available (imputed dates cannot be used for the duration computation).

See Section 14 for the calculation of treatment duration.

The time since an event (eg time since first diagnosis) will be calculated as reference date minus date of event.

12 Trial Subjects

The subsections in this section include specifications for reporting subject disposition and treatment/study discontinuations. Additionally, procedures for reporting protocol deviations are provided.

